5.9 Baseline 2 session

Upon return to the clinic, the RA will address any queries or concerns the participant may have since the first baseline visit. If they wish to continue in the study, the RA will administer the NetSCID-5 on a laptop to confirm a DSM-5 diagnosis of OCD and detect any co-morbid conditions, some of which may exclude the participant from the study (see section 4.2). Eligible participants' blood pressure, height and weight will be collected and self-reported questionnaires collected by the RA (if applicable). An ACL pathology slip will be given to participants consenting to provide a blood sample for the study and who prefer to complete the test off-site. They will be advised to complete the blood test at a time and ACL location of their convenience, ideally within the next four weeks. Alternatively, the blood sample can be collected on-site by an RA trained in venipuncture (see section 6.4). The participant will also be emailed a URL link containing the

DQES v3.2 and advised to complete online at home before the Week-4 study visit. If no internet is available at home, the participant will be provided with a laptop where they will complete the questionnaire on site with the RA. Upon conclusion of the final baseline session, the CGI-S will be completed by the RA.

The participant will be dispensed one IP container which will provide sufficient capsules for the following 4-weeks, as well as dosage instructions (verbally, on the IP container and an accompanying handout) and various contact numbers (study landline and after hours study mobile number, and TMC contact details in the event of an emergency/mental distress). They will also be provided with an estimated appointment calendar for the remaining follow-up visits.

A follow-up phone call will be conducted 7-10 days after the baseline 2 session to ensure compliance, tolerance and address any queries from the participant. The date and time of the Week-4 follow-up session will also be re-confirmed.

5.10 Follow-up visits

Participants will be required to attend follow-up visits at Week-4, 8, 12, 16, 20 and 24. In these sessions, participants will be asked to provide an overview since their last visit, particularly any noticeable changes in their OCD, mental health, functioning and/or quality of life. Changes in treatment (pharmacological and/or psychological), drug and alcohol consumption, medical conditions and the occurrence of side effects, if any, will also be ascertained. The Y-BOCS symptom checklist will be re-administrated by the RA to identify current obsessive and compulsive symptoms, followed by Y-BOCS severity scale (including question 11 regarding insight) and SIGHD-17. At each follow-up visit, the participant will also be asked to complete the DOCS, BAI, SDS, PGI-S, PGI-I and SAFTEE. Upon conclusion of each follow-up visit, the participants blood pressure will be taken and the CGI-I and CGI-S completed by the RA. In addition, at Week-12 and Week-20, the WHOQOL-BREF will also be completed by the participant.

Participants will also be reimbursed for travel expenses totaling \$140-\$160 in the form of Coles/Myer gift cards (\$20 at each scheduled visit; \$160 in total if all study visits are completed and if the baseline sessions are completed on separate days, reflecting additional travel costs incurred to the participant).

5.11 Final Study Visit

The final study visit will occur at Week-24, where the participants would have completed a single-blinded placebo run-out for the preceding 4-weeks (see section 5.12). In this final session, the RA will administer the Y-BOCS and SIGHD-17 and the participant will be given PGI-S, PGI-I, BAI, SDS and SAFTEE to complete. Participants will have the option of receiving three containers (120c in each) of NAC free of charge and advised to discuss with their treating doctor before use (a letter will also be provided to participants re-iterating this – see 'O-NAC Study completion letter' in appendix, approved by TMCREC 23 April, 2018).

5.12 Placebo run-out

The final four weeks of the trial will be reserved for the assessment of potential withdrawal effects and to investigate any sustained response that may occur after ceasing the NAC/placebo. This will be carried out my means of an additional four week single-blinded placebo run-out. The researchers will be aware that all participants will be transitioning onto placebo from Week-20 for the following four weeks, however, the participants will not be aware and continue under the assumption they may be receiving placebo or active treatment as they consented to in the baseline session. To uphold ethical standards whilst maintaining blinding, the PICF will state that the dose of NAC/placebo may change throughout the study to allow for titration and assessment of benefit/effect at various doses.

5.13 Withdrawal Visit

In the event of withdrawal, participants will be asked to detail their reasons for wishing to withdraw, or, if the decision of the researchers, the RA will record these reasons in the participants CRF. If willing, the participant will complete the Y-BOCS and SIGHD-17 with the RA and will complete the WHOQOL-BREF and SAFTEE. Finally, they will be asked to sign the withdrawal of consent form. If the participant specifies, all their data (including their stored genetic sample) can be destroyed and not included in the analysis. If not specified by the participant at the time of withdrawal, all their data will be used as outlined in the PICF.

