3.2.2 Secondary Outcome Measures

The Structured Interview Guide for the Hamilton Depression rating scale, 17 item (SIGHD-17), Beck Anxiety Inventory (BAI), Sheehan Disability Scale (SDS), Dimensional Obsessive Compulsive Scale (DOCS), Clinical Global Impression scales (clinician and patient rated) will be used as secondary outcome measures at each time point (baseline, W4, W8, W12, W16, W20 and W24. The World Health Organisation Quality of Life (WHOQOL-Bref) will also be used as a secondary outcome measure which will be completed by participants at baseline, W12 and W20.

O-NAC Protocol

Version 7.0 12 DEC 2018

These measures will investigate the therapeutic effects of NAC for improving mood, anxiety, and quality of life. In addition, both the rater's and participants overall perspective of OCD severity and improvement with time will be assessed.

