4.3.4 Handling of Withdrawals

Participants will be asked to attend an exit visit in person to sign a withdrawal of consent form. Reasons for withdrawal will be detailed and recorded in the patients CRF by the RA. If participants are withdrawn from the study due to worsening of OCD symptoms (i.e. Y-BOCS \geq 32) or mood (medical monitor's decision in cases of \geq 24 SIGHD-17), referral back to their treating doctor for appropriate care will be advised. In cases of strong suicidal ideation/intent, the participant will be seen by one of the medical investigators of the study.

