8 STATISTICAL CONSIDERATIONS

8.1 Sample Size Considerations

A sample size of 200 participants (100 participants in each arm) are to be recruited and intention-to-treat principles will be applied to all data. A large sample of 200 participants is powered to detect a potential small to moderate effect size (f = 0.15) difference between NAC and placebo beyond treatment as usual, approximating a clinically significant 3 point reduction on the YBOCS (using all post-baseline data via intention-to-treat analysis). Based on an ANOVA model over seven time-points, a two tailed analysis with alpha=0.05, beta=0.80, and a critical F of 3.78; 200 participants (not including drop-outs) are required to detect a small to moderate effect size difference in Y-BOCS scale score between treatment and placebo.

The primary efficacy analysis will assess mean treatment group differences for the primary outcome measure (Y-BOCS) using a mixed-effects model, repeated measures approach (MMRM). Results from the analysis of dichotomous data (e.g. demographics data) will be presented as proportions with 95% confidence interval, and Fisher's Exact *p*-value where appropriate. Analysis of covariance (ANCOVA) will also be used to compare differences between treatment means in changes from baseline to week 20 last observation carried forward (LOCF) endpoint. The ANCOVA model will assess confounding covariates including intervention type (medication or psychological care), as well as age, gender, weight, physical activity levels, smoking and alcohol consumption.

Non-parametric statistics will be used when assumptions for parametric methods are violated. Effect sizes will be calculated using Cohen's d. All tests of treatment effects will be conducted using a two-tailed alpha level of 0.05 and 95% confidence intervals. Data will be analysed via SPSS 23.0.

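### The withdrawal visit omits five of the seven secondary measures, so early leavers who attend it have no post-baseline DOCS, BAI, SDS, CGI or PGI (minor, cheap to improve)

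*Protocol*

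**What the plan says.** Protocol 3.2.2 names the secondary outcomes. SIGHD-17, BAI and SDS open the list, which continues: "Dimensional Obsessive Compulsive Scale (DOCS), Clinical Global Impression scales (clinician and patient rated) will be used as secondary outcome measures at each time point". The time points are given there as baseline and Weeks 4, 8, 12, 16, 20 and 24. WHOQOL-BREF "will also be used as a secondary outcome measure which will be completed by participants at baseline, W12 and W20".

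Protocol 5.10 sets the visits, "Participants will be required to attend follow-up visits at Week-4, 8, 12, 16, 20 and 24", and the self-report forms, "At each follow-up visit, the participant will also be asked to complete the DOCS, BAI, SDS, PGI-S, PGI-I and SAFTEE". The research assistant completes CGI-I and CGI-S at the end of each of these visits.

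For withdrawals, 4.3.4 states: "Participants will be asked to attend an exit visit in person". The content of that visit is in 5.13: "If willing, the participant will complete the Y-BOCS and SIGHD-17 with the RA and will complete the WHOQOL-BREF and SAFTEE". The assessment schedule in the Protocol Summary has no withdrawal column, and neither 4.3.4 nor 5.14 adds an outcome measure.

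On analysis, 8.1 says "intention-to-treat principles will be applied to all data". It names a mixed model for repeated measures for the Y-BOCS, and an ANCOVA on change to Week 20 with the last observation carried forward (LOCF).

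**The concern.** Withdrawal in this trial is related to treatment and outcome. The reasons in 4.3.3 include worsening, serious side effects, stopping the product and substantial treatment change. No outcome rating after withdrawal is described, so the exit visit is the last chance to record how the participant was doing.

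At that visit the Y-BOCS and SIGHD-17 are brought up to date, but anxiety, disability, symptom dimensions and both global impressions are not. For one participant, the primary and secondary outcomes may then refer to different dates, or the secondary outcome may have no post-baseline value at all. The missing values are likely to be informative ones. An analysis plan can choose how to handle a missing value, but it cannot recover one that was never collected, so the remedy lies in the protocol and the exit case report form.

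**Working it through.** The protocol states no figure on this point, so there is none to reproduce. The check sets the instrument lists and visit times side by side.

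**1. Which secondary measures are taken when** (Protocol Summary assessment schedule, 3.2.2, 5.8 to 5.10, 5.13)

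| Secondary measure | Baseline | First scheduled after baseline | At withdrawal |
|---|---|---|---|
| SIGHD-17 | yes | Week 4 | yes |
| WHOQOL-BREF | yes | Week 12 | yes |
| DOCS | yes | Week 4 | no |
| BAI | yes | Week 4 | no |
| SDS | yes | Week 4 | no |
| CGI | CGI-S only | Week 4 | no |
| PGI | PGI-S only | Week 4 | no |

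Collected at exit: 2 of 7. Not collected: 5 of 7 = 71%. If CGI and PGI are counted as one family, 2 of 6 are collected. The primary Y-BOCS and the SAFTEE side-effect checklist are also taken at exit.

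**2. What this means by time of leaving**

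- *Before Week 4, exit visit attended.* Y-BOCS, SIGHD-17 and WHOQOL-BREF have one post-baseline value each. DOCS, BAI, SDS, CGI and PGI have none.
- *Between two later visits, exit visit attended.* Visits are four weeks apart (for example 8 − 4 = 4), so the last value on the five measures can be up to four weeks old, while Y-BOCS and SIGHD-17 carry the exit date.
- *At a scheduled visit.* The full set in 5.10 is already planned for that day, so little is lost.
- *Exit visit or ratings refused.* Y-BOCS and SIGHD-17 are missing too, and a longer exit list would not help.

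The gap is confined to the first two groups.

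**3. What the analysis section fixes**

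Section 8.1 names the mixed model for the Y-BOCS only. It gives no model for the secondary outcomes and no rule for a participant with baseline data only. Three outcomes are possible for a leaver before Week 4:

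- Baseline treated as one of the repeated time points, or LOCF allowed to start from baseline: the participant stays in formally for DOCS, BAI, SDS, CGI-S and PGI-S, but contributes no information on change.
- Baseline used as a covariate, or LOCF requiring a post-baseline value: the participant is left out for those measures.
- CGI-I and PGI-I: no baseline exists, so the participant is lost under either approach unless values are imputed.

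For leavers between later visits, LOCF (if applied to the secondary measures) would carry forward a pre-exit value on the five measures.

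**4. Burden of the missing instruments** (6.2.4, 6.2.7 to 6.2.11)

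The exit visit already includes the 26-item WHOQOL-BREF. The omitted participant forms are DOCS (20 items), BAI (21), SDS (3 domains, expected to take 1 to 2 minutes) and PGI (2 parts): 20 + 21 + 3 + 2 = 46 responses. CGI-S and CGI-I are two ratings by the research assistant, who has just done the Y-BOCS. CGI, PGI and SDS are therefore nearly free; most of the added time is DOCS and BAI.

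**The case against.** A short exit set is a legitimate choice. It keeps the primary outcome, the depression scale that carries the suicidality item, side effects, and the quality-of-life form whose last value would otherwise be the oldest. It is voluntary, and a longer list may discourage some leavers. This stands as a reason for keeping the Y-BOCS and SIGHD-17 first. It does not explain leaving out the shortest instruments.

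Four stronger readings are tempting, and the protocol does not support them.

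- *That 5.13 contradicts 3.2.2.* It does not. Section 3.2.2 ties its measures to named visits, and the withdrawal visit is not one of them.
- *That early leavers certainly drop out of the secondary analyses, in breach of intention-to-treat.* Section 8.1 does not fix this, and the rule may properly sit in an analysis plan that is not at hand. It also does not say whether off-schedule exit values of the Y-BOCS and SIGHD-17 enter the analysis.
- *That the loss can be put at a definite number.* Assuming 10% to 30% withdraw and a fifth to a third of them leave before Week 4 gives 200 × 0.10 × 0.20 = 4 to 200 × 0.30 × 1/3 = 20 participants. Neither rate is in the protocol, and the count includes people who would also refuse the exit Y-BOCS.
- *That the lost cases before Week 4 are mainly those who worsened.* The scored triggers in 4.3.3 rest on ratings first scheduled after baseline at Week 4. The only scheduled contact before then is a phone call 7 to 10 days after baseline 2. When a trigger is met at a scheduled visit, the full set is planned for that visit. Leavers before Week 4 are more likely to be those with side effects, treatment changes or a wish to stop.

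One further limit stands. DOCS asks about the past month (6.2.4), so for a very early leaver it partly rates the period before treatment.

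**Conclusion.** The gap is real and minor. Five of the seven secondary measures are not taken at withdrawal. Participants who leave before Week 4 and attend an exit visit have no post-baseline value on them; those who leave between later visits have values up to four weeks old. The Y-BOCS is taken at exit, so the primary outcome is not affected.

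The effect on the secondary analyses depends on a handling rule the protocol does not state. Loss without imputation is certain only for CGI-I and PGI-I. The number of participants cannot be given, because the protocol states no withdrawal rate and its sample size of 200 excludes drop-outs. The conclusion rests on the instrument lists and visit times alone, and on no assumed rate. It is a cheap improvement, not an error that threatens the trial's main result.

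**What to change.** In 5.13, after the Y-BOCS and SIGHD-17, add CGI-S and CGI-I (completed by the research assistant), then PGI-S and PGI-I, SDS, BAI and DOCS. Keep the visit voluntary and record the assessment date. Note that DOCS has a one-month recall and so partly reflects the pre-treatment period in very early leavers. Add a withdrawal column to the assessment schedule so that the two agree.

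How exit values are assigned to time points, and how participants with baseline data only are handled on the secondary outcomes, belongs in the analysis plan.

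The cost is a wording change and an extended exit form, using instruments and staff the trial already has. The downside is added time for someone who is leaving. The protocol times only the SDS, so the total is not known. The order above protects the primary outcome if the participant stops part-way.

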5.14 Unscheduled Visit

Participants may be required to attend unscheduled study visits for the following reasons

- In the event of a SAE to assess impact, status and resolution of the event
- Necessity to withdraw participants from the study as per their wishes, or per protocol by the study investigators (see section 4.2)

All details of the visit will be recorded by the RA in the CRF, including reasons for the visit and future actions required regarding monitoring and following-up with the participant.

6 STUDY PROCEDURES/EVALUATIONS

6.1 Diagnostic assessments

The Structured Clinical Interview for DSM-5 (SCID-5) will be employed to confirm the presence of OCD and other comorbid mental health disorders as per DSM-5 criteria. The SCID-5 is a semi-structured, streamlined, clinician administrated instrument which assesses the presence of selected DSM-V mood disorders, anxiety disorders, substance use disorders, and personality disorders. The SCID-5 will be administered by the RA to the participant on an electronic tablet device or laptop using software called NetSCID (TeleSage, 2016).

The NetSCID is a relatively new tool that has been validated by 24 clinicians who administered the SCID (paper version) and/or NetSCID to 230 participants (Telesage, 2016). Validation studies are ongoing. When compared to the paper SCID, the NetSCID results in greater clinician satisfaction, fewer data entry and branching errors (TeleSage, 2016). The use of the NetSCID reduces the completion time by 30% compared to the paper version with data collected deidentified and scoring/coding of diagnoses instantaneous (TeleSage, 2016). Data from the NetSCID can be imported directly to a statistical package reducing data entry time and errors.

6.2 Clinical Evaluations

6.2.1 Qualitative review

At the beginning of each follow-up visit, participants will be asked to provide an overview of their month. Specifically, the RA will use the following semi-structured, open-ended questions to assist in gathering qualitative data:

- What, if any, changes have you noticed about your OCD over the past four weeks?
- What do you think has brought on these changes OR why do you think things have remained unchanged?
- Have you noticed differences in any other areas of your life over the past four weeks? (can prompt with...) For example, sleep, mood, energy, social life, work, stress...

Detailed notes will be taken by the RA during and after each visit, capturing as much information and narrative as possible provided verbally by the participant and also including the RAs own observations. The RA's impression of the participant's status and progress will also be detailed.

6.2.2 Yale Brown Obsessive-Compulsive Scale (Y-BOCS) – severity scale

The Y-BOCS (severity scale) was created in 1989 by Goodman and colleagues and is typically administrated as a 10-item instrument to provide a rating of severity regarding OCD symptoms. It is widely used in OCD clinical research and private practice and is well regarded as the gold standard for measuring the severity of both the obsessions and compulsions present in the disorder (Rapp, Bergman, Piacentini, & McGuire, 2016). Treatment sensitivity of the Y-BOCS has been demonstrated through its extensive use in clinical trials for OCD (Grabill et al., 2008). The Y-BOCS is a semi-structured, clinician administrated scale that asks the patients to reflect on the most prominent obsessive and compulsive symptoms separately over the past seven days, exploring frequency, impact/interference, distress caused and the person's effort to resist and ability to control the thoughts. A five point Likert scale ranging from 0-4 is used for each question, 0 equating to none or minimal impact/intensity and four of greatest severity. Scores are determined by the researcher based on the participant's self-reports as well as the researcher's own observations and interpretation during the session. The sum of the 10 items yields an overall score, which enables participant's OCD to be categorised as sub-clinical (0-7), mild (8-15), moderate (16-23), severe (24-31) and extreme (32-40). The Y-BOCS has demonstrated good criterion-related validity as patients diagnosed with OCD have received higher scores on the Y-BOCS compared to those with other anxiety disorders and healthy controls (Grabill et al., 2008). In addition, question 11 of the Y-BOCS will be administered at each visit which assesses the participant's insight into their obsessive and compulsive symptoms. A rating of excellent (=0), good (=1), mild (=2), poor (=3) and completely lacking insight (=4) can be determined on a Likert scale of 0 - 4, however, these scores are not included in the Y-BOCS total score.

6.2.3 Yale Brown Obsessive-Compulsive Scale (Y-BOCS) - symptom checklist

The Y-BOCS Symptom Checklist was developed by the same authors to augment the Y-BOCS severity scale (see section 6.2.2). It consists of 54 common obsessive and compulsive symptoms which are categorised into eight obsession subgroups, for example, aggressive obsessions (fear

Version 7.0 12 DEC 2018

might harm self or others; violent or horrific images), contamination obsessions (concerns or disgust with body waste or secretions; excessive concern with environmental contaminants) and obsessions with symmetry/exactness (concerns that another will have an accident unless things are in the right place); as well as seven compulsion categories including checking compulsions (checking locks, stoves, appliances; checking that did not/will not harm others), cleaning/washing rituals (excessive or ritualized handwashing) and repeating rituals (repeating or rewriting rituals). The checklist has been used to identify patients obsessive and compulsive symptoms in a dichotomous format (reported as 'yes' or 'no'), for symptoms endorsed at current as well as those experienced in the past. Current, more prominent symptoms are asked to be highlighted by the participant, thus enabling the Y-BOCS severity scale to reflect obsessions and related compulsions causing the most interference and/or distress to the patient. In this study, the symptom checklist will be administrated by the RA to the participant, rather than in self-report form.

